ASRS = Adult ADHD Self Report Scale; CTN SR = centanafadine sustained release; ET = early termination; P = placebo administration; R = randomization.

^aAll subjects will be required to participate in the 7-day follow-up period (follow-up telephone calls at 1, 3, and 5 days after the last dose of IMP, and in-clinic follow-up visits at 2 and 7 days after the last dose of IMP). Subjects who terminate early, decide to not enroll in Trial 405-201-00015, or who are not eligible to enroll in Trial 405-201-00015, will be required to participate in an additional follow-up telephone call 10 days after the last dose of IMP.

During the trial, administration of the investigational medicinal product (IMP) will be double-blinded. In other words, neither the investigator nor the subject will have knowledge of the treatment assignment (e.g., centanafadine SR 200 mg, 400 mg, or placebo). Treatment assignments will be based on a computer-generated randomization code provided by the Otsuka Pharmaceutical Development & Commercialization, Inc (OPDC) Biometrics Department. Sponsor personnel, including those involved in monitoring, data management, and data analysis, will not have access to the treatment code during the trial. The bioanalytical

SAP 405-201-00014

laboratory will also be sent the randomization code. The randomization will be stratified by trial site and designed to allocate subjects in a 1:1:1 ratio to centanafadine SR 200 mg/day or 400 mg/day or placebo.

4 Sample Size and Power Justification

The primary efficacy endpoint is the change from baseline at Day 42 in Adult ADHD Investigator Symptom Rating Scale (AISRS) total score. The trial will compare the placebo arm to the centanafadine dose arms, randomized at a ratio of 1:1:1, with an overall alpha of 0.05 for the primary endpoint.

Based on the results from Phase 2 centanafadine trials, it is reasonable to expect a treatment effect of 5 points with a standard deviation (SD) of 12.5 in the mean change from baseline to Day 42 on AISRS total score. The planned sample size of 405 evaluable subjects (135 in each treatment arm) will yield at least 90% power to detect the treatment effects at a 2-tailed significance level of 0.05.

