5.2 Handling of Missing Data

The mixed-effect model repeated measure (MMRM) assumes data are missing at random (MAR), which is a reasonable assumption in longitudinal clinical trials in MDD¹. However, the possibility of “missing not at random” (MNAR) data can never be ruled out. As sensitivity analyses, selection model², pattern-mixture model^{3,4,5,6}, and/or shared parameter model⁷ will be used to explore data missing mechanisms of MNAR and investigate the response profile of dropout patients by last dropout reason under MNAR mechanism for the following 3 scenarios: 1) Dropout reasons due to either AE or LOE as MNAR, 2) Dropout reasons due to either AE or LOE or subject withdrew consent as MNAR, 3) All dropouts as MNAR using

SAP 405-201-00014

both 1) Delta adjustment imputation method which is to departure from MAR assumption by progressively increasing the delta until conclusion from the primary analysis is overturned, and 2) Placebo based imputation methods in which missing data for both placebo and drug group are imputed based on the imputation model derived from placebo data. If drug improved outcomes prior to dropout, this benefit is carried into subsequent imputed values, but will diminish over time in accordance with the correlation structure. Details are provided in [Section 8.1.3 Sensitivity Analysis](#). The observed-cases (OC) data set will consist of actual observations recorded at each visit during the double-blind treatment period and no missing data will be imputed. MMRM, Wu-Bailey, and pattern-mixture model will be performed on the OC dataset.

The last-observation-carried-forward (LOCF) data set will include data recorded at a scheduled double-blind treatment period visit or, if no observation is recorded at that visit, data carried forward from the previous scheduled double-blind treatment period visit. Baseline data (e.g., the last visit of the single-blind placebo run-in period) will not be carried forward to impute missing values for the LOCF data set. The analysis of covariance (ANCOVA) analysis will be performed for the change from baseline to the end of the double-blind treatment period (Day 42, LOCF) in AISRS total score as sensitivity analysis. The ANCOVA_LOCF model includes treatment and study center as main effects, and baseline value as a covariate.

ANCOVA analysis with OC data will also be conducted on change from baseline for AISRS total score, as well as all continuous change from baseline efficacy endpoints.

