In this hypothetical strategy, the event of withdrawing IMP is considered missing at random (MAR), and the primary endpoint of the trial could be considered as a combination of the responses of on-treatment completers at Day 42 and the imputation of the endpoint to Day 42 following the trend in each treatment group using the MMRM method for subjects who withdraw IMP during the trial. All data collected during the trial treatment period will be used for statistical analysis. For the primary efficacy analysis, the treatment effect will be estimated using the MMRM method described below. Under the MAR assumption, MMRM provides an unbiased estimate of treatment effect for the treatment period. Analyses with missing values imputed by multiple imputation under MNAR and other methods will be performed as sensitivity analyses. The primary analysis will be performed on Efficacy Sample which includes all randomized subjects who took at least 1 dose of IMP in the double-blind treatment period and who have both a baseline for the double-blind treatment period and at least one post-randomization AISRS total score during the double-blind treatment period. The primary efficacy analysis will be performed by fitting a MMRM analysis with an unstructured (UN) variance covariance structure in which the change from baseline for the double-blind

SAP 405-201-00014

treatment period in AISRS total score at the scheduled double-blind treatment period visits will be the dependent variable based on the OC data set. The model will include fixed class effect terms for treatment, study center, visit day, and an interaction term of treatment by visit day. The model will also include the interaction term of baseline values for the double-blind treatment period of AISRS Total score by visit day as covariates. The primary comparison between centanafadine (400 mg TDD group or 200 mg TDD group) and placebo at Day 42 in the double-blind treatment period will be estimated as the difference between Least Squares (LS) means utilizing the computing software SAS procedure PROC MIXED.

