8.1.2 Technical Computation Details for Primary Efficacy Analysis

The SAS code for the PROC MIXED procedure to carry out the above MMRM analysis with an unstructured variance covariance structure is illustrated as follows:

```
proc mixed;
  class treatment center visit subjid;
  model change=treatment center visit treatment*visit baseline*visit / s cl
  ddfm=kenwardroger;
  repeated visit /type=un subject=subjid r rcorr;
```

SAP 405-201-00014

```
lsmeans treatment*visit / pdiff cl alpha=0.05 slice=visit;
run;
```

where baseline is the last AISRS Total score prior to the first dose of double-blind IMP in the double-blind treatment period.

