treatment difference between centanafadine and Placebo from the primary analysis of MMRM model until conclusion of the primary analysis is overturned. When $\delta=0$ it is MAR. When $\delta > 0$ it is MNAR.

- 1) Using Monte Carlo Markov Chain (MCMC) methodology from PROC MI to impute the intermittent missing data to a monotone missing pattern;
- 2) Using a standard MAR-based multiple imputation approach from PROC MI to impute the monotone missingness data
- 3) For patients in the treated group and with a dropout reason of AE or LOE or subject withdrew consent, a delta will be added for all the values after the dropout time.
- 4) Using MMRM model in the primary analysis to analyze the completed data using PROC MIXED on the multiple imputed data
- 5) Obtaining the overall results using PROC MIANALYZE.

Placebo Based Imputation Methods

Similar to “Standard” multiple imputations, except parameters for imputation model obtained from only the placebo (control) group. Missing data for both placebo and drug group are imputed based on the imputation model derived from placebo data. If drug improved outcomes prior to dropout, this benefit is carried into subsequent imputed values, but will diminish over time in accordance with the correlation structure.

In addition, model based MNAR methods such as the shared parameter model ([Wu and Baily, 1989](#)) and random coefficient pattern mixture model ([Hedeker D, Gibbons RD, 1997](#)) will be also performed.

LOCF and OC Analyses

Change from baseline of the double-blind treatment period for the AISRS total score will be evaluated using ANCOVA with baseline of the double-blind treatment period value as covariate and treatment and, in LOCF analyses, study center as main effects. For the OC analyses, study center will not be included in the model.

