 PROGRAM: /opt/sas/Data/DAP/EB1020/P40520100014/STAT/Program.dev/DOC_STAT/stat1.sas
 OPDC, NEW DRUG APPLICATION, IND # 119,361 CENTANAFADINE STAT-4.2 FINAL

CENTANAFADINE
 PROTOCOL 405-201-00014

1 OF 6

STAT-4.3
 Proc GLM Output for Change from Baseline to Day 42 in AISRS Total Score, OC
 (Efficacy Sample)

 ----- Parameter Code=AI SRSTOT Analysis Visit (N)=42 -----

The GLM Procedure

Class Level Information

Class	Levels	Values
TRTPN	3	1 2 3

Number of Observations Read	421
Number of Observations Used	421

SOURCE: GLMOUT; TABLE: stat1c.lis; RUN: 31AUG2020 08:32; ANALYSIS DATASET CREATED: 16JUN2020 08:14
 PROGRAM: /opt/sas/Data/DAP/EB1020/P40520100014/STAT/Program.dev/DOC_STAT/stat1.sas
 OPDC, NEW DRUG APPLICATION, IND # 119,361 CENTANAFADINE STAT-4.3 FINAL

CENTANAFADINE
 PROTOCOL 405-201-00014

2 OF 6

STAT-4.3
 Proc GLM Output for Change from Baseline to Day 42 in AISRS Total Score, OC
 (Efficacy Sample)

 ----- Parameter Code=AISRSTOT Analysis Visit (N)=42 -----

The GLM Procedure

Dependent Variable: CHG Change from Baseline

Source	DF	Sum of Squares	Mean Square	F Value	Pr > F
Model	3	1943.84121	647.94707	5.86	0.0006
Error	417	46112.61010	110.58180		
Corrected Total	420	48056.45131			

R-Square Coeff Var Root MSE CHG Mean
 0.040449 -109.2314 10.51579 -9.627078

Source	DF	Type III SS	Mean Square	F Value	Pr > F
TRTPN	2	1249.405044	624.702522	5.65	0.0038
BASE	1	618.365333	618.365333	5.59	0.0185

SOURCE: GLMOUT; TABLE: stat1c.lis; RUN: 31AUG2020 08:32; ANALYSIS DATASET CREATED: 16JUN2020 08:14
 PROGRAM: /opt/sas/Data/DAP/EB1020/P40520100014/STAT/Program.dev/DOC_STAT/stat1.sas
 OPDC, NEW DRUG APPLICATION, IND # 119,361 CENTANAFADINE STAT-4.3 FINAL

Until the information herein is released by Otsuka to the public domain, the contents of this document are Otsuka confidential information and should not be duplicated or re-distributed without prior written consent of Otsuka.

CENTANAFADINE
 PROTOCOL 405-201-00014

3 OF 6

STAT-4.3
 Proc GLM Output for Change from Baseline to Day 42 in AISRS Total Score, OC
 (Efficacy Sample)

 ----- Parameter Code= AISRSTOT Analysis Visit (N)=42 -----

The GLM Procedure

Level of TRTPN	N	-----CHG-----		-----BASE-----	
		Mean	Std Dev	Mean	Std Dev
1	140	-10.7071429	10.8359224	37.5857143	6.75041775
2	140	-11.0571429	10.7125768	38.7642857	6.95578090
3	141	-7.1347518	10.1624096	37.6453901	6.34837972

SOURCE: GLMOUT; TABLE: stat1c.lis; RUN: 31AUG2020 08:32; ANALYSIS DATASET CREATED: 16JUN2020 08:14

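### The supportive observed-case ANCOVA drops study center without a stated reason, although randomisation is stratified by site and both the primary MMRM and the LOCF ANCOVA keep it

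*SAP*

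**What the plan says.** SAP Section 3 sets the design: "The randomization will be stratified by trial site". Center then appears in two of the three continuous-endpoint models that bear on this point:

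- **Primary MMRM, fitted to OC data** (SAP 8.1.1 and 8.1.2): "The model will include fixed class effect terms for treatment, study center, visit day, and an interaction term of treatment by visit day". The code agrees: "model change=treatment center visit treatment*visit baseline*visit".
- **LOCF ANCOVA** (SAP 5.2): "The ANCOVA_LOCF model includes treatment and study center as main effects, and baseline value as a covariate".
- **OC ANCOVA** (SAP 5.2): "ANCOVA analysis with OC data will also be conducted on change from baseline for AISRS total score", and also on the other continuous change-from-baseline efficacy endpoints. SAP 8.1.3.1 gives its model: "For the OC analyses, study center will not be included in the model".

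SAP 5.2 defines the OC data set as recorded observations for which "no missing data will be imputed". Neither document gives a reason for leaving center out. Small centers are already pooled under SAP 8.1.1 and 10.2.

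**The concern.** Site is the stratification factor, so the usual course is to carry it into the analysis, as the other two models do. Being an OC analysis does not explain the omission, because the MMRM uses the same OC records with pooled center.

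What is at stake is interpretation. The LOCF and OC ANCOVAs stand together in the section on sensitivity to the missing-at-random assumption and are listed as adjacent tables (CT-5.2.6.1 and CT-5.2.6.2). A reader will compare them to see whether missing-data handling changes the answer. As planned, data set and model change together, and a difference caused by the model could be blamed on dropout.

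**Working it through.** **1. What the output labelled OC contains.** STAT-4.3 is titled "Proc GLM Output for Change from Baseline to Day 42 in AISRS Total Score, OC". It uses 421 records and repeats the LOCF arm means and SDs of STAT-4.2. STAT-5.3 does the same for CGI-S against STAT-5.2. The true AISRS OC counts at Day 42 (STAT-4.7) are 113 + 102 + 123 = 338. The error sums of squares in STAT-4.3 and STAT-4.2 differ by 46112.61 − 39250.46 = 6862.15, which is the center sum of squares in STAT-4.2. So STAT-4.3 appears to be the LOCF data refitted without center. The planned OC ANCOVA is not shown, but the pair isolates the effect of dropping center on identical records.

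**2. Effect on identical LOCF records** (error df 379 with center, 417 without; STAT-4.2, 4.3, 5.2, 5.3):

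| Contrast with placebo | With center: estimate (SE), p | Without center: estimate (SE), p | Variance ratio (SE ratio squared) |
|---|---|---|---|
| AISRS 200 mg | −3.880 (1.2200), 0.0016 | −3.583 (1.2547), 0.0045 | 1.058 |
| AISRS 400 mg | −4.047 (1.2280), 0.0011 | −3.719 (1.2576), 0.0033 | 1.049 |
| CGI-S 200 mg | −0.301 (0.1157), 0.0096 | −0.284 (0.1169), 0.0154 | 1.020 |
| CGI-S 400 mg | −0.236 (0.1167), 0.0437 | −0.216 (0.1174), 0.0668 | 1.012 |

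The AISRS estimates shrink by (3.880 − 3.583)/3.880 = 7.7% and (4.047 − 3.719)/4.047 = 8.1%. The CGI-S 400 mg estimate shrinks by 8.7%.

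**3. Why CGI-S 400 mg crosses 0.05.**
- Changing only the SE and df: 0.23616/0.11739 = 2.012 on 417 df, p = 0.0449.
- Changing only the estimate: 0.21571/0.11668 = 1.849 on 379 df, p = 0.0653.

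Almost all of the move comes from the shift in the estimate. Center itself is F = 1.33, p = 0.0997 in that CGI-S model, and F = 1.74, p = 0.0053 in the AISRS model.

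**4. What a true OC ANCOVA would gain.** This cannot be computed from the documents. A projection has two parts.
- Residual variance without over with center, from the LOCF fits: AISRS 110.582/103.563 = 1.0678; CGI-S 0.95886/0.93116 = 1.0298.
- The design cost of fitting center, from the center-by-arm counts in STAT-4.5.2: on all 421 subjects the contrast variance factor is 1.0095 (200 mg) and 1.0154 (400 mg).

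Check on AISRS: 1.0678/1.0095 = 1.058 and 1.0678/1.0154 = 1.052, against 1.058 and 1.049 observed in step 2.

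Randomly reducing the arms to 113/102/123 (4,000 draws) gives mean factors of 1.0327 (95% range 1.019 to 1.049) and 1.0433 (1.027 to 1.064). The projected contrast variance without over with center is then:
- AISRS: 1.0678/1.0327 = 1.034 and 1.0678/1.0433 = 1.023.
- CGI-S: 1.0298/1.0327 = 0.997 and 1.0298/1.0433 = 0.987.

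**5. Cost in df and sparsity.** With 338 records, treatment and baseline leave 338 − 4 = 334 error df; 38 center parameters leave 296. Fifteen of the 39 pooled centers have a single subject in some arm. In the same draws about 6 centers (95% range 3 to 10) have an empty arm at Day 42.

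**The case against.** The strongest reply is that this is a preference about a prespecified supportive analysis outside the fixed testing sequence. It affects no confirmatory claim, and leaving out a stratification factor tends to make standard errors too large. All of that stands.

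The benefit in precision is also slight. On true OC data it is projected at 2 to 3% of variance for AISRS and nothing for CGI-S, and the CGI-S projection borrows the AISRS counts. That stands too. The larger figures, including the CGI-S p-value, come from LOCF records and show only that the model change can move results; they do not estimate its effect on the planned analysis.

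A reader can already set the center-adjusted MMRM on OC data beside the center-adjusted LOCF ANCOVA, and delta-adjusted and placebo-based imputation address missing data more directly. This lessens the harm, but the two ANCOVA tables will still be read as a pair.

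Sparse centers could be a reason, and protocol Section 7.3.2.2 uses the same convention for its OC CMH tests. Pooling ensures an evaluable subject in every arm, not a Day 42 value. But neither document offers sparsity as the reason, and the MMRM carries pooled center on the same records, so sparsity does not require the omission.

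On scope, SAP 8.1.3.1 states the omission for AISRS only. SAP 5.2 excludes center from OC models after a sentence on CGI Change and the categorical variables, but STAT-5.3 applies the omission to CGI-S, a continuous endpoint.

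Finally, the 421-record discrepancy is an output fault rather than a fault in the plan. It matters here because the analysis has to be rerun in any case.

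**Conclusion.** The concern holds and is minor: an improvement the sponsor could make, not one the trial depends on. The omission is explicit and unexplained, and it departs from the stratified design and from both companion models. On identical records, dropping center moves the AISRS estimates by about 8% toward zero and is enough to take a nominal CGI-S p-value across 0.05. The primary and key secondary MMRMs keep center, and CGI-S 400 mg is p = 0.0245 there (STAT-5.1), so no confirmatory conclusion changes.

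The case rests on consistency and interpretability rather than precision. The OC projection assumes random dropout within arm and the LOCF residual-variance ratios. The textual finding needs neither assumption.

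**What to change.** Keep pooled center, under the existing rule in SAP 10.2, as a fixed effect in the OC ANCOVA for AISRS and the other continuous endpoints, and run it on true OC records. This takes one model term and a matching wording change in SAP 5.2 and 8.1.3.1. The protocol's efficacy analysis section (7.3) names no ANCOVA, so it needs no amendment. The price is the 38 error df and the few centers with an empty arm at Day 42; those centers still inform the remaining comparison.

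If center is to stay out, state the reason and add the LOCF ANCOVA without center, so that the pair can be compared on one model. STAT-4.3 and STAT-5.3 appear to hold that fit already, under the wrong label, and should be relabelled.

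The OC CMH tests and the subgroup MMRMs, which also omit center, are outside this request: their cells are sparse, and the protocol also plans OC CMH tests without center.

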8.1.3.2 Per Protocol Analyses

Per Protocol analysis will be performed using the Per Protocol Sample.

8.1.3.3 Other Sensitivity Analyses

The following analyses will be performed to evaluate of the sensitivity of the results due to the impact of COVID-19.

1. A MMRM analysis (the same model for the primary efficacy analysis) based on the pre-COVID Efficacy Sample using all OC data set during the double-blind treatment

SAP 405-201-00014

- period . The pre-COVID Efficacy Sample comprises those subjects in the Efficacy Sample who completed or discontinued from the study before March 13, 2020, the National Emergency Announcement on COVID-19¹¹.
2. A MMRM analysis (the same model for the primary efficacy analysis) based on the Efficacy Sample using pre-COVID data set. The pre-COVID data set consists of actual observations recorded at each visit during the double-blind treatment period before March 13, 2020, the National Emergency Announcement on COVID-19¹¹.
 3. A MMRM analysis (the same model for the primary efficacy analysis) based on the non-COVID Efficacy Sample using all OC data set during the double-blind treatment period. The non-COVID Efficacy Sample comprises those subjects in the Efficacy Sample who had no COVID-19 related PDs.
 4. A MMRM analysis (the same model for the primary efficacy analysis) based on the Efficacy Sample using non-COVID data set. The non-COVID data set consists of actual observations recorded at each visit during the non-COVID treatment period which represents the time period where subjects did not have any COVID-19 related PDs during the double-blind treatment period. For each subject, the non-COVID treatment period starts from randomization and ends on the Day 42/ET date or the date before the first COVID-19 related PD (if present), whichever occurs earlier.
 5. A MMRM analysis (the same model for the primary efficacy analysis) based on the Efficacy Sample excluding the assessments performed remotely.

8.1.3.4 Sensitivity Analyses for Violation of Normality Assumption

The primary endpoint MMRM analysis is a maximum likelihood method that relies on normality assumption. Residual analyses will be carried out to examine model assumption.

In the case of gross violations of the normality assumptions, nonparametric van Elteren test⁸ (van Elteren, 1960) will be performed to compare treatment effect at Week 14 on both LOCF dataset and Multiple Imputation (MI) data. The van Elteren test is a generalized CMH procedure useful for stratified continuous data in non-normal setting. It belongs to a general family of Mantel-Haenszel mean score tests. The test is performed via SAS procedure PROC FREQ, by including CMH2 and SCORES=MODRIDIT options in the TABLE statement. The stratification factor is trial center.

In addition, other methods that are robust to distributional assumption will also be performed to provide different views on the primary efficacy result, these include generalized estimating equations (GEE), weighted GEE (WGEE), and MI-robust regression⁹.

SAP 405-201-00014

For MI-van Elteren test and MI-robust regression, imputation datasets will be generated with SAS MI procedure, each dataset will be analyzed, then an overall estimate is derived with SAS MIANALYZE procedure.

